## **17.6 Adjudication Committee**

All reported adverse events and clinical endpoints, including any bleeds requiring intervention, will be adjudicated by an independent Adjudication Committee that will be blinded to study treatment.

### **17.6.1 Adverse Event and Clinical Endpoint Reporting**

When any problem or event which, in the opinion of the local investigator, was unanticipated, places subjects or others at a greater risk of harm than was previously known or recognized, and was possibly related to the research procedures occurs, the site coordinator and/or PI will notify the Project Coordinator within 48 hours of becoming aware of the event. The site coordinator will record the information in the source documentation and will forward all relevant medical information to the Project Coordinator who will prepare the documents for Adjudication Committee review.

When a MACE is suspected, the site coordinator and/or PI will notify the Project Coordinator within 48 hours of becoming aware of the event. The site coordinator will record the information in the source documentation and in the eCRF and will forward all relevant medical information to the Project Coordinator who will prepare the documents for Adjudication Committee review.

When any bleed requiring diagnostic study or intervention (e.g. doctor's visit, change in medication, ER visit, hospitalization) is suspected, the site coordinator will record the information in the source documentation and in the eCRF and will forward all relevant medical information to the Project Coordinator who will prepare the documents for Adjudication Committee review.

When any death occurs, the site coordinator will record the information in the source documentation and in the eCRF and will forward all relevant medical information to the Project Coordinator who will prepare the documents for Adjudication Committee review.

### **17.7 Monitoring**

See Appendix H.

### **17.8 Informed Consent Procedures**

All eligible patients will provide written informed consent using procedures reviewed and approved by the Mayo Clinic IRB and respective institutional IRBs/REBs at other U.S.A. and international sites. Informed consent will be undertaken by study personnel in person with the patient. The patient has the option of declining participation. No study procedures will be conducted until the signed documents have been provided. Any modifications to the protocol that warrants revision to the informed consent document will be reviewed and approved by each site's respective IRB/REB. The revised consent form will be shared with previously enrolled subjects and a new signature obtained as directed by each site's respective IRB/REB.

### **17.9 Confidentiality**

Subjects enrolled in the study will be identified with a study number. Within each participating site, subjects will also be identified by their site-specific registration number and their name but these subject identifiers will not be released outside of the participating site. Genotype data will be collected specifically for the research protocol. Clinical and demographic data will also be collected from the subject's medical records for the purposes of the research protocol but all data will be de-identified before being released outside of that participating site. Any publications will exclude any kind of subject identifiers that could be correlated with the specific subject.

## **APPENDICES**

### **A. Ticagrelor and Clopidogrel Dose Justification and Side-effects**

#### **Ticagrelor Dose Justification (normal dosage, oral route)**

##### **Acute coronary syndrome - Thrombosis; Prophylaxis**

For patients with ACS, unstable angina, NSTEMI, or STEMI, the recommended ticagrelor loading dose is 180 mg orally once plus aspirin (usually 325 mg), followed by a maintenance dose of ticagrelor 90 mg twice daily with aspirin 75 to 100 mg once daily. Maintenance doses of aspirin greater than 100 mg daily are not recommended.

##### **Percutaneous coronary intervention - Thrombosis; Prophylaxis**

- a. For patients with ACS, unstable angina, NSTEMI, or STEMI undergoing PCI, the recommended maintenance dose of ticagrelor is 90 mg twice daily with aspirin 75 to 100 mg once daily. Maintenance doses of aspirin greater than 100 mg daily is not recommended.
- b. Subjects who have received a loading dose of clopidogrel may be started on ticagrelor maintenance dosing. Ticagrelor should be discontinued at least 5 days prior to surgery, when possible. Ticagrelor is contraindicated in patients with severe hepatic impairment.

#### **Clopidogrel Hydrogen Sulfate Dose Justification (normal adult dosage, oral route)**

Clopidogrel should be discontinued 5 days prior to elective surgery, if an antiplatelet effect is not desired.

1. Acute ST segment elevation myocardial infarction - Percutaneous coronary intervention - Thrombosis; Prophylaxis
  - a. Initial loading dose, 300 mg or 600 mg ORALLY plus aspirin once prior to or at the time of PCI
  - b. Maintenance, 75 mg ORALLY plus aspirin once daily
  - c. Bare metal stents: duration of therapy for at least 12 months
  - d. Drug-eluting stents: duration of therapy for at least 12 months; continuation of therapy beyond 15 months may be considered
2. Acute ST segment elevation myocardial infarction - Thrombosis; Prophylaxis
  - a. Optional loading dose of 300 mg ORALLY, followed by 75 mg ORALLY once daily in combination with aspirin 75 to 325 mg, with or without thrombolytics
3. Cerebrovascular accident, Recent - Thrombosis; Prophylaxis
  - a. 75 mg ORALLY once daily
4. Myocardial infarction, Recent - Thrombosis; Prophylaxis
  - a. 75 mg ORALLY once daily
5. Non-ST segment elevation myocardial infarction, acute - Percutaneous coronary intervention - Thrombosis; Prophylaxis
  - a. Initial loading dose, 300 mg to 600 mg with aspirin 75 to 325 mg as soon as possible; maintenance, 75 mg ORALLY plus aspirin 75 to 325 mg once

- daily
- b. Alternate loading dose, 600 mg ORALLY, followed by 150 mg maintenance dose daily for 6 days, then 75 mg daily in low bleeding risk patients
  - c. Bare metal stents: duration of therapy for at least 1 month and ideally up to 12 months
  - d. Drug-eluting stents: duration of therapy for at least 12 months
6. Non-ST segment elevation myocardial infarction, acute - Thrombosis; Prophylaxis
    - a. Loading dose, 300 mg ORALLY once; maintenance, 75 mg ORALLY once daily with aspirin 75 mg to 325 mg ORALLY once daily
  7. Percutaneous coronary intervention - Thrombosis; Prophylaxis - Unstable angina
    - a. Initial loading dose, 300 mg to 600 mg with aspirin 75 to 325 mg as soon as possible; maintenance, 75 mg ORALLY plus aspirin 75 to 325 mg once daily
    - b. Alternate loading dose, 600 mg ORALLY, followed by 150 mg maintenance dose daily for 6 days, then 75 mg daily in patients with low bleeding risk
    - c. Bare metal stents: duration of therapy for at least 1 month and ideally up to 12 months
    - d. Drug-eluting stents: duration of therapy for at least 12 months
  8. Peripheral arterial occlusive disease - Thrombosis; Prophylaxis
    - a. 75 mg ORALLY once daily

#### **Dosage in Hepatic Insufficiency**

1. Dosage adjustments for clopidogrel are not necessary in patients with hepatic impairment.
2. No dosage adjustment is necessary for mild to moderate cirrhosis (Child-Pugh class A or B) based on a 10-day multiple-dose study in subjects with cirrhosis and matched controls. The mean peak concentration, time to peak concentration, and area under the concentration-time curve (AUC) for clopidogrel's major metabolite (SR 26334) did not differ statistically between groups. The geometric mean for AUC in patients with cirrhosis failed to reach the predetermined threshold of clinical significance (1.5 times above the geometric mean in controls). The mean percentage inhibition of platelet aggregation and mean bleeding time prolongation factor were statistically similar between cirrhotics and controls.

#### **Dosage in Geriatric Patients**

1. No dosage adjustments are necessary.
2. Clopidogrel 75 milligrams/day for 10 days was associated with statistically similar reductions of 55% to 57% in adenosine diphosphate (ADP)-induced platelet aggregation among healthy young, healthy elderly, and elderly patients with intermittent claudication. All three groups also experienced statistically equivalent prolongation of bleeding time (by a factor of 1.47 to 1.59). For clopidogrel's metabolite, SR 26334, the average peak concentration and the extent of absorption were significantly higher in the two elderly groups compared with the young volunteers, which did not translate into an age-related pharmacodynamic difference.
3. Loading Dose: In the FAST-MI Registry analysis of patients 75 years of age and older with acute myocardial infarction (n=791; mean age 81 +/- 4 years old), a clopidogrel loading dose (greater than or equal to 300 mg) was not associated with an increased risk of major bleeding or transfusion but did not significantly decrease 12 month mortality when compared with standard clopidogrel therapy (less than 300

mg). There were 466 patients who received a clopidogrel loading dose of at least 300 mg (300 mg in 384 patients, 375 mg in 5 patients, 450 mg in 16 patients, 600 mg in 60 patients, and 900 mg in 1 patient) and 325 patients who received standard clopidogrel therapy (75 mg in 287 patients, 150 mg in 27 patients, and 225 in 11 patients). One year survival (80.7% compared with 73.5%;  $p=0.02$ ) and one year event free survival (77.3% compared with 68.6%;  $p=0.009$ ) were higher in patients treated with a clopidogrel loading dose

### 18.1.1 Ticagrelor Side Effects

- Cardiovascular effects may include atrial fibrillation (4.2%), bradyarrhythmia (Holter-detected), chest pain (3.1%), hypertension (3.8%), hypotension (3.2%), loss of consciousness, and syncope.
- Endocrine/Metabolic effects may include gynecomastia (0.23%).
- Gastrointestinal effects may include diarrhea (3.7%), and nausea (4.3%).
- Hematologic effects may include bleeding, major (4.5%), and bleeding major and minor (8.7%).
- Musculoskeletal effects may include backache (3.6%), and chest pain, non-cardiac (3.7%).
- Neurologic effects may include dizziness (4.5%) and headache (6.5%).
- Renal effects may include increased uric acid level and raised serum creatinine level (7.4%).
- Respiratory effects may include cough (4.9%) and dyspnea (13.8%).
- Other side effects may include fatigue (3.2%).

### 18.1.2 Clopidogrel Side Effects (<2% unless otherwise stated)

- Cardiovascular effects may include coronary artery stent thrombosis, hypotension, and vasculitis.
- Dermatologic effects may include acute generalized exanthematous pustulosis, bullous dermatosis, contusion, erythema multiforme, erythematous rash, fixed drug eruption, lichen planus, pruritus, Stevens-Johnson syndrome, and urticaria.
- Gastrointestinal effects may include colitis, gastrointestinal hemorrhage (2%-2.7% with aspirin), and pancreatitis.
- Hematologic effects may include agranulocytosis, aplastic anemia, major bleeding (0.8% to 3.7%), non-major bleeding (3.6% to 5.1%), granulocytopenic disorder, hemolytic uremic syndrome, leukemia, leucopenia, neutropenia, pancytopenia (severe), postoperative hemorrhage, thrombocytopenia, and thrombotic thrombocytopenic purpura.
- Hepatic effects may include hepatitis, hepatotoxicity, liver failure, and liver function tests abnormal (up to 3% of patients).
- Immunologic effects may include anaphylactoid reaction, immune hypersensitivity reaction, and serum sickness due to drug.
- Musculoskeletal effects may include arthralgia, acute arthritis, myalgia, and tendinitis.
- Neurologic effects may include disorder of taste, epidural hematoma, intracranial hemorrhage, and loss of taste.
- Ophthalmic effects may include intraocular hemorrhage (0.05%).
- Psychiatric effects may include confusion.
- Renal effects may include abnormal renal function, hematuria, kidney disease, and serum creatinine raised.
- Respiratory effects may include bronchospasm, interstitial pneumonia, non-cardiogenic pulmonary edema, and respiratory tract hemorrhage.

- Other effects may include angioedema, drug withdrawal, rebound effect, and postoperative infection.

## **B. Clinical Trial Management Systems (CTMS)**

CTMS is the Mayo Clinic Research Committee-endorsed institutional resource for clinical data management. CTMS is a robust institutional effort initiated in 2009 to address emerging changes within the data and statistical coordinating centers affiliated with National Cancer Institute (NCI)-funded cooperative groups. In 2009, NCI selected Medidata Rave (<http://www.mdsol.com/>) as the required data collection tool for all cooperative studies. To capitalize on Mayo Clinic and the NCI's investment in Medidata Rave, Mayo Clinic formalized a three-tier data management infrastructure with the Medidata Rave product as the premier system.

Medidata Rave is a product for multi-center clinical trials conducted under 21 CFR Part 11 requirements. This web-based system provides ease of use coupled with an integrated randomization module (Medidata Balance), custom reporting, robust data validation routines, and straightforward integration with SAS.

### **Electronic Data Capture**

Medidata Rave allows for data collection in multisite studies. During the course of the data entry into Medidata Rave, the system provides real-time within-CRF and inter-CRF data consistency verification. Medidata Rave is flexible in nature so that all data can be entered even if "required" fields and or other consistency checks requirements are not satisfied. The system uses an internal "flagging" or "query" system to distinguish the valid from the invalid data thereby ensuring compliance with the FDA guidance document "Computerized Systems Used in Clinical Trials." All data discrepancy issues are tracked and audited by the system to ensure the highest quality data is available for analysis and study reporting.

Contained within the CTMS initiative at Mayo Clinic is a diverse set of administrative and technical personnel to support the development and implementation of clinical trials in Medidata Rave. While the time necessary to program Medidata Rave's eCRFs has been directly budgeted, the CTMS initiative supports protocol independent activities such as software/server maintenance, data standards, institutional system integrations, SAS data, and training of study personnel through institutional resources.

The dedicated virtual private network (VPN) connection between Mayo Clinic and Medidata Rave provides the conduit for data connectivity. Clinical trial data hosted in Medidata Rave is accessible when needed for SAS using the SAS OnDemand Connection, in combination with Mayo Clinic's SAS Pipeline program, which creates a common and direct combination of the metadata (labels, formats, etc.) and data (raw values) into SAS datasets on a scheduled (nightly) basis. This process removes the need to separately label and format the entire clinical trial database separately in SAS.

### **Medidata Balance**

Randomization encounters challenges in complex multisite clinical studies in which random assignment to study drug must be completed prior to the baseline visit and a subject can fail to attend the baseline visit or be deemed ineligible for the study based on the final inclusion/exclusion criteria assessed at the baseline visit. It is possible that some individuals will not receive active treatment after treatment assignment has been established. Medidata Balance uses a novel multidimensional dynamic allocation algorithm minimizing imbalances

across multiple dimensions including overall study, sites, factors, and cross-factor strata. It is also highly flexible with extensive weighting and can be applied to most randomization scenarios including unbalanced designs. The algorithm in Medidata Balance represents a novel multidimensional dynamic allocation algorithm for treatment assignments.

### C. Statistical Calculations

*Likelihood Method for Real Time Estimation of Treatment Effect and Event Rates:* At any point in time during the TAILOR-PCI trial, there are two sources of data on the treatment effect: 1) data from subjects with 1 complete year of follow-up and TaqMan processing completed (“complete” data), and 2) the data on those with less than 1 year of follow-up or without TaqMan processing, half of whom have been genotyped using SPARTAN (“incomplete”). The *complete* subjects have complete endpoint and genotype data, while the *incomplete* subjects have incomplete endpoint and incomplete genotype data. Nevertheless, both sets of data have information on the treatment effect, and this information can be quantified. The analysis of the subjects who have undergone TaqMan is straightforward; a good approximation is a binomial comparison between the two LOF groups, in terms of their one year event rate. To recover the information in the prospectively randomized subjects who have not had TaqMan analysis complete, we propose the following simplified yet highly accurate approach.

There are 3 groups: 1) prospectively genotyped, loss of function carriers (PG-LOF) who are given ticagrelor, 2) prospectively genotyped, wild type subjects (PG-WT) who are given clopidogrel and 3) conventional therapy (CT) who are given clopidogrel. Let us simplify the primary endpoint to a binary outcome  $X$  (yes or no) with a probability that depends on: genotype( $G$ ), treatment( $Rx$ ), and follow-up time. Specifically, we assume that, for a subject with genotype  $G$ , treatment  $Rx$ , and observed for  $t$  years, the probability of an event is:

$$\begin{aligned} \Pr\{X = 1|G, Rx, t\} &= \lambda_{G,Rx} * \frac{[1 - S(t)]}{[1 - S(1)]} \\ &= w(t) * \lambda_{G,Rx} \end{aligned}$$

where  $S(\cdot)$  is the overall underlying survival curve for freedom from events,  $t$  is time in years. Note that if the subject experiences the primary endpoint, the value of  $t$  is not tied to the event time itself, but rather reflects the visit date (roughly 1 month, 6 months, or one year) representing the effective amount of follow-up for that patient (time from randomization to last follow-up date). To calculate  $S(\cdot)$ , we simply use the Kaplan-Meier curve for the entire study population. This fraction therefore represents the fraction of a “risk year” to which that subject was exposed, i.e. it is an estimate of the proportion of events occurring within a year that have occurred at the follow-up time for the specific individual. Note that we consider  $w(t)$  to be a fixed quantity, rather than a parameter, though technically it is estimated from the entire data set.

We further assume that the event rates (1-year probabilities) are:

$$\lambda_{WT,CL} = \lambda_1$$

$$\lambda_{LOF,TIC} = \lambda_2$$

$$\lambda_{LOF,CL} = \lambda_3$$

We also assume that the rate of wild type subjects exposed to clopidogrel ( $\lambda_1$ ) is the same whether they are in the conventional therapy or the prospective genotyping group. This is a fundamental assumption, but one which will also be ultimately tested.

The treatment effect of interest can be expressed as  $\lambda_2/\lambda_3$ , that is, the relative risk associated with

ticagrelor in LOF subjects. The trial's primary hypothesis is that this number is substantially less than 1.0. (Relative risk reduction is 1 minus this quantity). Finally, let  $\alpha$  be the population prevalence of the LOF genotype in the population being randomized. We can now define the likelihood contributions of members of each of the three groups of "incomplete" subjects.

For those in the PG-WT and PG-LOF groups, the likelihood contributions, respectively, are:

$$L(\lambda_1|X, t) = [\lambda_1 * w(t)]^X * [1 - \lambda_1 * w(t)]^{(1-X)}$$

$$L(\lambda_2|X, t) = [\lambda_2 * w(t)]^X * [1 - \lambda_2 * w(t)]^{(1-X)}$$

For those in the CT group, the likelihood contribution is a weighted average of the likelihood contributions that would be obtained under (WT, CLOP) and (LOF, CLOP) conditions, weighted by the probability of each genotype, namely:

$$L(\lambda_1, \lambda_3, \alpha|X, t) = (1 - \alpha) * L_1(X, t) + \alpha * L_3(X, t)$$

where  $L_1$  and  $L_3$  have the obvious definitions parallel to the 'known-genotype' likelihoods spelled out above. If this were the only data available, then the 4 parameters ( $\lambda_1, \lambda_2, \lambda_3, \alpha$ ) would not be identifiable, i.e.  $\alpha$  and  $\lambda_3$  would be completely confounded. However, we have one further piece of data: the numbers of LOF and WT subjects in the PG group. These numbers can be put into a binomial likelihood with  $\alpha$  as the only parameter. The random variable corresponding to this proportion is statistically independent (at least uncorrelated), with all the other likelihood pieces. Therefore, the overall likelihood is the product of all the conditional likelihood pieces for the members of the 3 groups, along with this binomial likelihood for the prevalence of LOF. This serves to identify both  $\alpha$  and therefore  $\lambda_3$  as parameters. Thus in this complete likelihood, all 4 parameters are identified. Thus, the *incomplete* data provides a likelihood that *is* informative about the treatment effect (subject to the null hypothesis assumption regarding the effect of knowledge of genotype on the WT/CLOP response). The likelihood from these data can be combined with the simple TaqMan binomial data to derive a combined likelihood which incorporates both pieces of information.

*Estimation of Information Time:* We can also estimate the proportion of total study information contained in the current data. First, we estimate the expected information at the end of the trial as the

inverse of the expected square of the standard error of the hazard ratio of interest. Our expected power of 85.8% implies that our expected z-score at the end of the trial is 3.031. Given a minimum detectable effect size of 0.50, the expected standard error at study end is 0.2287 ( $\log(0.5)/3.031$ ). Thus the expected final information is 19.1. Second, the available information in the current data is calculated using a profile likelihood approach to estimate the standard error of the current estimate of the treatment effect. The ratio of the current information to the expected final information is the estimated information time.

*Calculation of conditional power:* Conditional power is a function of the current effect estimate z-score and information time. Its formula is:

$$CP(t, Z_t) = 1 - \Phi\left[\frac{\Phi^{-1}(0.975) - Z_t \sqrt{t}}{\sqrt{(1-t)}}\right] - (\Phi^{-1}(0.975) + \Phi^{-1}(P_0)) * \sqrt{(1-t)}$$

where  $t$  is information time,  $Z_t$  is the current z-score,  $\Phi$  is the cumulative Gaussian distribution function,  $\Phi^{-1}$  is its inverse and  $P_0$  is the unconditional study power under initial study assumptions.  $Z_t$  will be calculated from the log of the estimated effect and its estimated standard error.

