**Table 1. Schedule of Assessments to be performed during the study**

	Screening/Randomization V1 & 2			Treatment (Phone Interview)			EOT/Safety Endpoint
	Pre-Procedure**	Index Procedure	Post-Procedure	V3	V4	V5	
				30 Days (-2/+7 days)	6 months (+/-28 days)	12 months (+/- 28 days)	
Assessment of Eligibility	x						
Informed Consent	x						
Genotyping Survey 	x				x		
Hospitalization Intake 	x						
Medications	x		x	x	x	x	x
Vitals	x						
β-HCG Pregnancy test 2*	x						
Creatinine*	x		x				
CK/CK-MB*	x		x				
Troponin T/I*	x		x				
Angiogram/PCI procedure*		x					
Genotyping			x 			x	x 
Randomization			x				
Hospitalization Dismissal			x				
Electrocardiogram*	x		x				
Follow-up outcomes	x			x	x	x	x
Study Endpoint Events			x	x	x	x	x 
Death Event Form 							
End of Treatment						x	x 
Education Level & Computer Literacy***				x			

 Hospitalization forms to be completed for each hospitalization during study participation

 Only in women of childbearing potential (local urine or serum pregnancy test)

 Complete only if randomized to prospective genotyping

 Complete only if subject dies after randomization and before 12 month treatment phase

 Complete only if subject terminates participation prior to 12 months

 Completed for first 1,000 subjects only

\*Data only will be collected from these clinically indicated tests/procedures

\*\*If subject is screened/randomized post-procedure, these items will be collected post-procedure

[figure not shown]
\*\*\*This information will be collected once at any of these phone interviews, unless the patient has already completed these visits. Because these questions were not part of the original consent, the patient will be given the chance to opt out of these questions.

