## 15.8 Monitoring for Futility and Efficacy

Both efficacy and futility monitoring require three estimates: 1) a best current estimate of the treatment effect, as well as 2) uncertainty of the estimate (standard error and/or confidence interval), and 3) an estimate of what proportion of the study's final information is currently in hand, that is, the current value of "information time".

Information time is critical both in assessing conditional power (futility) as well as in doing interim testing using group sequential approaches. Appendix C details how to

construct a combined likelihood combining the information from the complete and the incomplete subject data, which produces the first two required estimates, using likelihood calculations, and specifically, using the profile likelihood method to get down to the one-dimensional likelihood for the treatment effect parameter.

Appendix C also details how to estimate information time (the third required measure). Once we have a current z-score (effect divided by standard error) for the treatment effect, as well as our current estimate of information time, we can then do standard calculations for conditional power (futility) and efficacy

**Futility Monitoring:** We propose that this assessment be based on our calculation of conditional power, as described in Appendix C. In addition to the conditional power calculation, we will provide the modified unconditional power calculation based on current estimates of event rates and the estimate and 95% CI of the average event rate in LOF subjects. We specifically propose that at the time of DSMB reviews, that consideration be given to stopping the trial if the ratio of conditional power to initial power falls below the proportion of remaining information time. For example, if the initial power is 85%, and the proportion of remaining information time is 40%, then the conditional power should exceed 34% ( $0.85 \times 0.4$ ). The basis for the moving target of conditional power is the “sunk cost” argument. The initial study design is assumed to equate the expected utility of a positive result with the cost of the entire study. By equating the ratio between conditional power and initial power, the cost-benefit ratio is maintained. This means that the bar for conditional power for continuing gets progressively lower, as more of the total study costs become a “sunk cost.”

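### Appendix C defines a complete subject with no exception for death; programmed literally, with no term for TaqMan-complete wild-type subjects, it biases the interim relative risk toward 1

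*Combined protocol and SAP*

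**What the plan says.** Appendix C (Statistical Calculations) estimates the interim treatment effect from two sources. The first is "data from subjects with 1 complete year of follow-up and TaqMan processing completed". The second is "the data on those with less than 1 year of follow-up or without TaqMan processing". Neither definition mentions subjects who die within the year.

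For the first source, the appendix says that "a good approximation is a binomial comparison between the two LOF groups, in terms of their one year event rate". It later calls this part simple TaqMan binomial data. It writes no term for wild-type subjects whose TaqMan result is in. For the second source it writes separate terms for prospective-arm wild-type subjects (rate λ1) and prospective-arm LOF subjects (λ2). Conventional-arm subjects enter as a mixture of λ1 and λ3, weighted by the LOF prevalence α. The effect of interest is λ2/λ3.

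The same paragraph also points the other way. It says complete subjects have both endpoint and genotype data in full, and it introduces the mixture as a way to use "prospectively randomized subjects who have not had TaqMan analysis complete", with no reference to length of follow-up. In Table 1 the end-of-treatment genotyping cell carries the footnote "Complete only if subject dies after randomization and before 12 month treatment phase", so genotyping after an early death is foreseen.

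The estimate, its standard error and the information time feed Section 15.8. There the DSMB is asked that "consideration be given to stopping the trial if the ratio of conditional power to initial power falls below the proportion of remaining information time".

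**The concern.** CV death is part of the primary outcome (Section 12.1). A patient who dies on day 90 has a known outcome and can have a TaqMan result, but never reaches one year of follow-up. Under the explicit split that patient stays incomplete for good, while one-year survivors of the same cohort move to the complete set.

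The effect differs by arm. A prospective-arm LOF death keeps its genotype and still counts toward λ2. A conventional-arm LOF death falls into the unknown-genotype mixture. If TaqMan-complete wild-type subjects have no term, λ1 is informed only by incomplete subjects, and these include every wild-type death but not the matching survivors. λ1 is inflated, the mixture credits most conventional-arm deaths to wild type, and λ3 is too low.

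At stake is the advice given to the DSMB. A relative risk biased upward lowers conditional power and also weakens the z-score used against the efficacy boundary.

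**Working it through.** **1. The plan's own constants.** z = 1.960 + Φ⁻¹(0.858) = 3.031. SE = ln 2 / 3.031 = 0.2287. Information = 1/0.2287² = 19.1. All three agree with Appendix C.

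**2. Inputs.**
- From Section 15.2.2: overall LOF event rate 4.5% and hazard ratio 0.50, taken as 6% on clopidogrel and 3% on ticagrelor. LOF prevalence is 59% in Korea and 28% in North America. With the observed 30% Korean share, 0.30 × 59 + 0.70 × 28 ≈ 37%.
- Assumed, because the documents do not give them: wild-type rate 4.5%; 30% of one-year risk accrued by 1 month and 65% by 6 months; uniform accrual of 1,054 a year (5,270/5); TaqMan lag of 3 months; fatal share d of primary events from 10% to 40%.

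**3. Mechanism, at 4 years of accrual with d = 30%.**
- Mature subjects: (4 − 1.25) × 1,054 = 2,898. Recent subjects: 1.25 × 1,054 = 1,318.
- Prospective wild type, mature: 2,898 × 0.5 × 0.63 = 913, with 913 × 0.045 × 0.30 = 12.3 deaths left as incomplete.
- Prospective wild type, recent: 1,318 × 0.5 × 0.63 = 415. Mean weight w = (1×0 + 5×0.30 + 6×0.65 + 3×1)/15 = 0.56, so 232 risk-years and 232 × 0.045 = 10.5 events.
- Crude λ1 from these subjects: (10.5 + 12.3)/(232 + 12.3) = 9.3%, against a true 4.5%.
- Conventional LOF, complete: 2,898 × 0.5 × 0.37 = 536 subjects and 32.2 events, of which 9.7 are fatal. The binomial sees 22.5/526.5 = 4.3%, against a true 6%.
- Maximising the full likelihood on expected counts gives λ1 = 11.5%, λ2 = 3.0% and λ3 = 4.5%, so RR = 3.0/4.5 = 0.67.
- LOF share credited among conventional-arm events of unknown genotype: 0.37 × 0.045/(0.63 × 0.115 + 0.37 × 0.045) = 19%. The true share is 0.37 × 0.06/(0.63 × 0.045 + 0.37 × 0.06) = 44%.

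The follow-up time t assigned to a death does not matter within this likelihood. For an event, w(t) is a fixed multiplier and drops out of the maximisation.

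**4. Large-sample RR when the true RR is 0.50, at 2 to 5 years of accrual.**

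| Fatal share | Deaths incomplete, no wild-type term | Deaths complete | Deaths incomplete, wild-type term added |
|---|---|---|---|
| 10% | 0.53-0.54 | 0.50 | 0.50 |
| 20% | 0.57-0.60 | 0.50 | 0.50 |
| 30% | 0.63-0.67 | 0.50 | 0.50 |
| 40% | 0.70-0.77 | 0.50 | 0.50 |

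Varying the wild-type rate, accrual period and TaqMan lag widens the rows only slightly: 0.61-0.68 at 30% and 0.68-0.78 at 40%.

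**5. Futility guideline.** CP = 1 − Φ[(1.960 − Z√t)/√(1−t) − 3.031√(1−t)], with the drift term read inside Φ and Z = −ln(RR) × √t/0.2287. The threshold is 0.858 × (1 − t).

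| Information time | Threshold | CP at RR 0.59 | CP at RR 0.77 | RR needed to cross |
|---|---|---|---|---|
| 40% | 0.515 | 0.844 | 0.658 | 0.908 |
| 60% | 0.343 | 0.843 | 0.461 | 0.829 |
| 80% | 0.172 | 0.865 | 0.163 | 0.767 |

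The biased value alone crosses only at RR 0.77 and the 80% look, and narrowly. Otherwise the bias acts by making a chance crossing more likely. Simulated chance of meeting the criterion when the true RR is 0.50:

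| Fatal share | Single look at 4 years (400 runs) | Any of the three looks (250 runs) |
|---|---|---|
| Deaths classed as complete | about 6% | 7-8% |
| 20% | 14% | 20% |
| 30% | 23% | 34% |
| 40% | 40% | 59% |

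**The case against.** The strongest reply is that the definition of complete is not enough to cause the bias. Adding TaqMan-complete wild-type subjects restores 0.50 even with deaths left as incomplete, and Appendix C never says those subjects are discarded. It offers the LOF comparison only as an approximation. This stands: the bias needs both literal readings together. But both are what the appendix writes out, and it states no wild-type term for a programmer to include.

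Second, the paragraph's other wording and Table 1 indicate that a genotyped death was meant to count as complete. This also stands. It makes the problem a conflict in the specification and not evidence of a wrong intention.

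Third, Appendix C ties t for event subjects to a visit date and not to the event date. That leaves follow-up after a death unclear, but it does not say that a death is credited with a full year. As shown above, the choice of t does not change the estimate while deaths remain incomplete.

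A reader might infer that the plan as written turns a true 0.50 into roughly 0.59-0.77 and so triggers false futility. The documents do not support that. The range depends on a fatal share they do not state for this trial, and at 10% the bias is small. The guideline asks only for consideration of stopping. In the 4-year simulations most trials did not meet it, even at 40% fatal. The DSMB also receives the average LOF event rate and a modified unconditional power.

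**Conclusion.** The concern holds in a limited form. Appendix C's explicit split conflicts with its own description of complete subjects. If the split is followed literally with only the LOF binomial for complete data, the interim relative risk is biased toward 1 when ticagrelor is beneficial. With a true value of 0.50, the size runs from about 0.54 at a 10% fatal share to 0.70-0.77 at 40%. It rests on the assumed fatal share above all, and less on wild-type rate, accrual, event timing and TaqMan lag.

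The consequence is a higher chance of an unwarranted futility signal, not an automatic stop. The final analysis in Section 15.5 is a Cox model from randomization with TaqMan genotype. It does not use this split and is unaffected.

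**What to change.** Make two changes to Appendix C.

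1. Define a complete subject, in both arms, as one with a TaqMan result and a known one-year primary-endpoint status: either one year of follow-up, or a primary event or death before one year, once the subject's one-year anniversary has passed. All others are incomplete. The anniversary condition keeps deaths and survivors of the same enrolment cohort together.
2. State that TaqMan-complete wild-type subjects contribute a binomial term for λ1.

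Either change removes the bias under the assumptions used here; making both also settles the conflicting wording. The cost is a few lines of text and a small change to the interim program. No new data are needed: blood for DNA is taken at baseline, genotyping after early death is already foreseen, and deaths are already adjudicated. If an interim estimate has already been produced, confirm which rule its program used.
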